6.5. Investigational Sites

The clinical study will be conducted at up to six (6) investigational sites in the US. Sites will have a clinical environment that is representative of the normal conditions of use of the study devices in the target population. The governing Institutional Review Board (IRB) for each participating site will review and approve the protocol, informed consent form, and any other applicable study-related documents prior to enrolling subjects. Additional information on site selection is included in **Section 9.1**.

A site contact list containing contact information for site staff participating in this study will be maintained in the Investigator Site File (ISF) and Trial Master File (TMF).

6.6. Target Enrollment

Approximately 60 subjects (30 per group) indicated to undergo a TIPS procedure who are eligible for the study and agree to participation will be enrolled. Subjects will be enrolled in the study once and have one TIPS procedure.

Each investigational site will be limited to enroll up to 16 subjects.

6.7. Study Duration

The study enrollment period is anticipated to take approximately 6 months. Enrolled subjects are followed for 30 days from the TIPS procedure requiring individual subject participation for approximately 1 month.

Upon completion of all enrolled subjects, study closure, including data analysis and preparation of the clinical study report, is estimated to take up to an additional 6 months.

Total study duration is expected to be approximately 13 months.

7. SUBJECT SELECTION

7.1. Study Population

Subjects undergoing an interventional TIPS procedure for refractory variceal bleeding, refractory ascites, and/or hydrothorax are the target population for this study because cases tend to be non-emergent and scheduled.

The study population represents the intended population for the study devices in terms of age (adult population), sex (both male and female), procedure (transjugular liver access for diagnostic or interventional procedures).

7.2. Inclusion Criteria

Subjects must meet all inclusion criteria listed below to be eligible for enrollment in the study:

1. At least 18 years of age at the time of the TIPS procedure
2. TIPS procedure initiated for refractory variceal bleeding and/or refractory ascites/hydrothorax
3. Willing and able to provide written informed consent and Health Insurance Portability and Accountability Act (HIPAA) authorization, either individually or through a legally authorized representative (LAR)
4. Willing and able to comply with the study procedures and follow up schedule

7.3. Exclusion Criteria

Subjects meeting any of the following exclusion criteria will not be eligible for enrollment in the study:

1. Known active malignancy
2. Model for End-Stage Liver Disease (MELD) score ≥ 18 at time of screening
3. History of polycystic liver disease
4. Active bleeding from any source
5. Pulmonary hypertension, heart failure, severe tricuspid valve dysfunction, right to left cardiopulmonary shunt
6. Chronic, occlusive portal vein thrombosis or complete portal vein thrombosis of the main or target portal vein on prior CT examination
7. Active or uncontrolled hepatic encephalopathy
8. Systemic infection/sepsis
9. Biliary obstruction
10. Uncorrectable coagulopathy
11. Any diminutive or partially thrombosed right portal vein
12. Hepatic vein thrombosis (i.e., no Budd-Chiari syndrome)
13. Known sensitivity to contrast or serious contrast reaction such as anaphylaxis
14. Pregnant women or women who are planning to become pregnant

7.4. Screening

Potential subjects will be identified from non-emergent cases scheduled for a TIPS procedure. All potential subjects will be contacted remotely or in-person by the treating physician (i.e., the PI) or

investigational site staff. During this contact, the PI will verify eligibility of the subject based on the inclusion and exclusion criteria listed in **Sections 7.2 and 7.3**.

Eligibility of potential subjects can be determined from historical laboratory, imaging, and echocardiography results previously taken per standard of care. Labs must have been taken within 30 days prior to the scheduled TIPS procedure. Imaging and echocardiography must have been obtained within 90 days prior to the scheduled TIPS procedure.

Subjects that fail to meet the study screening criteria will be documented as a screen failure on the study screening and enrollment log. Screen failures can be re-screened for study eligibility at the discretion of the Investigator. If a subject is re-screened, a new entry should be recorded on the study screening and enrollment log.

7.5. Informed Consent

Subjects must be fully counseled and informed of their study options, risks, and benefits, and have every opportunity to ask questions about participation in this study. The subject will sign the IRB-approved ICF prior to initiation of the TIPS procedure. For subjects who are unable to provide written consent, consent may be obtained from the subject's legally authorized representative (LAR) per the institution/IRB policies, if allowed.

A copy of the signed statement of informed consent will be provided to the subject and/or LAR.

The PI or qualified designee is responsible for obtaining written informed consent from each subject prior to participation in the clinical study. Should the Investigator delegate the responsibility of conducting the informed consent process to a designee, the Investigator must ensure and document appropriate training of the authorized designee.

If new information regarding the investigational device becomes available and/or changes to the protocol affect a subject's future health and medical care, subjects will be provided with the information and may be asked to sign a revised informed consent form.

The consent process must be documented in the subject's medical record. The original, fully signed consent form will be kept in the site's study file or subject medical record per the institution policy. A fully signed copy must also be provided to the subject and/or LAR.

Subjects that decline participation in the study, do not provide consent, or withdraw consent prior to initiation of the TIPS procedure will be documented as a screen failure on the study screening and enrollment log.

Once the study-specific informed consent form (ICF) is signed, the subject is considered enrolled.

7.6. Subject Identification

Enrolled subjects will be assigned a unique subject identification (ID) number. The subject ID number will be included on all study documentation relating to that subject. If an enrolled subject is withdrawn, the subject ID number will not be re-used in this study.

The investigational site will maintain a study screening and enrollment log linking the assigned study subject ID and the subject's name, alternative identification (e.g., medical record number)

and/or contact information. This log will be maintained only at the investigational site and used during monitoring to assure the correct identity of the subject records used for source document verification.

7.7. Randomization

Randomization will occur after an eligible subject has signed the ICF and prior to initiation of the TIPS procedure. Subjects will be randomly assigned at a 1:1 ratio into one of the two study groups (Scorpion or Cook) via a centralized randomization service.

Once the randomization assignment is received, the physician will determine the model he/she wants to use based on preference, training, and the subject case before beginning the procedure.

7.8. Blinding

This is an open-label study. Blinding is not utilized.

8. STUDY PROCEDURES

8.1. Schedule of Assessments

The procedures and assessments for this study are outlined in the schedule of assessments (**Table 6**).

Study data will be collected at the following 5 time points: screening, TIPS procedure, hospital discharge, Day 7 follow up, and Day 30 follow up. Subjects will be exited from the study following completion of the Day 30 follow up visit or when they withdraw from the study. More detailed descriptions of the assessments are provided in subsequent sections.

Table 6. Schedule of Assessments

Procedure / Assessment	Screening ¹ (Day -90 to Day 0)	TIPS Procedure (Day 0)	Hospital Discharge	Day 7 ⁷ (± 1 day)	Day 30 (± 7 days)
Informed Consent	X				
Demographic Data	X				
Inclusion/Exclusion Criteria	X				
Medical History	X				
Physical Exam	X		X		X
Labs: CBC, CMP, PT, INR	X ²		X		X
MELD Score	X		X		X
Child-Pugh Score	X		X		X
Randomization		X ⁴			
TIPS procedure		X			
Duplex Ultrasound					X
CT or MRI	X ³				
Echocardiography	X ³				
Portogram		X ⁵			
AE Assessment		X ⁶	X	X	X
Concomitant Medications	X	X	X		X
Study Exit					X ⁸

¹ Assessments to be done prior to any study related procedure

² Within 30 days prior to the procedure

³ Preprocedural imaging via standard of care obtained within 90 days prior to the procedure

⁴ Randomization must be completed prior to TIPS procedure

⁵ At portal vein access and following stent deployment

⁶ Adverse Events will be assessed during and after the procedure

⁷ Phone call if subject has been discharged, in-person if subject is still in the hospital on Day 7

⁸ Study Exit may occur prior to Day 30 as Early Exit

8.2. Screening Assessment (Day -90 to Day 0)

The data captured for the Screening assessment may be gathered over the course of more than one day. However, the data must be obtained within 90 days prior to the TIPS procedure date except as noted below. All data must be documented in the subject's medical record and reported on the appropriate eCRF.

The following activities will be performed for the Screening assessment:

Collection of demographic information

Review of inclusion/exclusion criteria

Collection of clinically significant medical history data, including indications for the procedure

Perform physical examination, including at a minimum:

- Evaluation for hepatic encephalopathy
- Evaluation for presence of ascites

Perform blood draw, if not performed as standard of care within 30 days prior to the procedure, for clinical evaluation of the following labs:

- Complete Blood Count (CBC)
- Comprehensive Metabolic Panel (CMP)
- Prothrombin Time (PT)
- International Normalized Ratio (INR)

Determine MELD Score

Determine Child-Pugh Score

Perform radiologic evaluation to assess hepatic venous patency, portal venous patency, and hepatic arterial patency and excluding potential masses in the liver.

- Computed Tomography (CT) or Magnetic Resonance Imaging (MRI) obtained within 90 days prior to the procedure can be used.

Perform Echocardiography, if not performed as standard of care within 90 days prior to the procedure, to assess cardiopulmonary status

Record Concomitant Medications (only rifaximin, lactulose, and medications which are an anticoagulant, antiplatelet, or diuretic will be recorded)

8.3. TIPS Procedure (Day 0)

The TIPS procedure will be completed in a clinical setting with adequate angiographic equipment and institutional facilities, physiologic monitoring equipment, and support personnel.

Transjugular liver access will be obtained using either the Scorpion set or Cook set per randomization assignment and physician choice of model. The procedure will be performed in accordance with the Scorpion IFU or the Cook IFU. Refer to the current IFU included with the device for techniques and methods for pre-procedure preparation and directions for use. The specific model and treatment details (e.g., access site, access side, stent, etc.) will be determined by the physician based on the condition of the subject.

A minimum of 5 needle passes should be attempted with the initial device assigned through randomization before selecting the alternative manufacturer set. If an alternative manufacturer set is selected, the information will be recorded as part of the study records.

The following procedure data are to be collected and recorded in the subject's medical record or other applicable source documents which will be reported on the appropriate eCRF:

Jugular access site
Number of needle passes
Hepatic vein used for access
Access device used
Portal vein access site
Imaging used
Alternate access sites/techniques used
Sheath used
Stent used, dilated to what size
Pressure gradient measurements: pre- and post-delivery of stent
Presence of residual varices
Adverse events (during and post procedure)
Record Concomitant Medications (only rifaximin, lactulose, and medications which are an anticoagulant, antiplatelet, or diuretic will be recorded)

A portogram must be obtained to confirm creation of the parenchymal tract between the hepatic vein and an intrahepatic branch of the portal vein upon portal vein access and following stent deployment.

8.4. Hospital Discharge

At discharge from the hospital, usually between 1-7 days post TIPS procedure, subjects will be evaluated, and the following activities will be performed:

Physical examination, including at a minimum:

- Evaluation for hepatic encephalopathy
- Evaluation for presence of ascites

Blood draw, for clinical evaluation of the following labs:

- Complete Blood Count (CBC)
- Comprehensive Metabolic Panel (CMP)
- Prothrombin Time (PT)
- International Normalized Ratio (INR)

Determine MELD Score

Determine Child-Pugh Score

Adverse event assessment

Record Concomitant Medications (only rifaximin, lactulose, and medications which are an anticoagulant, antiplatelet, or diuretic will be recorded)

All data must be documented in the subject's medical record and reported on the appropriate eCRF.

8.5. Day 7 (+/- 1 Day) Follow-Up

Adverse events will be assessed seven days (\pm 1 day) after the TIPS procedure. New adverse events or updates to previously reported adverse events will be documented in the subject's medical record and reported on the appropriate eCRF.

If the subject has been discharged from the hospital, the 7 Day post-procedure follow up will be conducted via phone call with designated study staff.

If the subject remains in the hospital, the 7 Day post-procedure assessment can be done in person by designated study staff.

If the visit window overlaps with hospital discharge, the 7 Day follow up assessment of adverse events should be done as part of hospital discharge.

8.6. Day 30 (+/- 7 days) Follow Up

The 30 Day follow up assessment will be the final study visit and subjects will exit the study after completion of this follow up visit.

Thirty days (\pm 7 days) after the TIPS procedure, subjects will return to the clinic for a follow up visit during which the following activities will take place:

Physical examination, including at a minimum:

- Evaluation for hepatic encephalopathy
- Evaluation for presence of ascites

Blood draw, for clinical evaluation of the following labs:

- Complete Blood Count (CBC)
- Comprehensive Metabolic Panel (CMP)
- Prothrombin Time (PT)
- International Normalized Ratio (INR)

Determine MELD Score

Determine Child-Pugh Score

Duplex Ultrasound to assess hepatic venous patency, portal venous patency, and shunt status

Adverse event assessment

Record Concomitant Medications (only rifaximin, lactulose, and medications which are an anticoagulant, antiplatelet, or diuretic will be recorded)

8.7. Study Completion

A subject will exit the study after completion of the Day 30 follow up assessments or an event that precludes further participation in the study.

The clinical study will be considered completed when all subjects have exited the study.

8.8. Subject Withdrawal

Subjects have the right to withdraw from the clinical study at any time and for any reason without prejudice to their future medical care by the investigational site staff or institution. If a subject decides to withdraw, all study-specific procedures will be stopped. The data captured for those participants up to the day of withdrawal will be kept in the database, as permitted by national laws and regulations. Whenever possible, the site staff should obtain written documentation from the subject that wishes to withdraw consent for future study activities and contacts. If the site staff is unable to obtain written documentation, all information regarding the subject's withdrawal must be documented in the subject's medical record and reported on the appropriate eCRF.

Withdrawal of a subject from the study may also occur at the discretion of the Principal Investigator or the Sponsor. Reasons for physician and/or Sponsor-directed subject withdrawal include, but are not limited to:

- The subject is not adhering to the study requirements
- Subject enrollment in another study that conflicts with this study's outcomes
- It is in the best interest for the safety or welfare of the subject to be withdrawn

If a subject is amenable at the time of withdrawal, the assessments specified at the final study visit (Day 30) should be collected and documented in the subject's medical record and reported on the appropriate eCRF.

In general, any ongoing or unresolved AEs/SAEs at study end will proceed with standard of care per institution policy.

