6.3. Study Design

This is a prospective, multicenter, randomized comparative post-market study in the United States (US). The study consists of a one-day intervention in subjects indicated to undergo a TIPS procedure with the aim of collecting real world safety and effectiveness data on the Scorpion set and comparator devices.

The Cook Transjugular Liver Access set was chosen as the comparator device because it is commonly used.

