6.4.2. Primary Safety Endpoint

The primary safety endpoint is a composite of major complications associated with the procedure or study device and defined as complications resulting in an unplanned increase in the level of care, prolonged hospitalization, permanent adverse sequelae, or death.¹⁰

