11.4. Missing Data

Missing data will not be imputed unless otherwise specified.

For categorical variable, if unknown and missing data may be presented as a separate category and the denominator might include unknown and missing category where deems appropriate.

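### After a treated subject is withdrawn by the investigator or sponsor, or exits early, nothing requires safety data to be collected up to Day 30

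*Combined protocol and SAP*

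**What the plan says.** **Who may end participation, and why.** Section 8.8 gives the power to both parties: "Withdrawal of a subject from the study may also occur at the discretion of the Principal Investigator or the Sponsor". Its list of reasons is open-ended and includes "The subject is not adhering to the study requirements" and "It is in the best interest for the safety or welfare of the subject to be withdrawn". Section 8.7 lets a subject leave after Day 30 "or an event that precludes further participation in the study". Section 8.1 treats withdrawal as study exit, and a note to Table 6 provides for exit before Day 30. None of these provisions is confined to subjects not yet treated.

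**What remains to be stopped.** Section 6.3: "The study consists of a one-day intervention". Sections 6.7 and 8.6 follow subjects to Day 30. Section 7.8 states that there is no blinding.

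**What is collected on leaving.** Section 8.8 asks for the Day 30 assessments at the time of withdrawal if the subject is willing. It keeps data recorded up to then, a statement made for subjects who themselves decide to withdraw. As a general rule, "any ongoing or unresolved AEs/SAEs at study end will proceed with standard of care per institution policy".

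**What the data are for.** The primary safety endpoint in Section 6.4.2 counts complications that lead to an unplanned step-up in care, "prolonged hospitalization, permanent adverse sequelae, or death". Section 11.3.3 bases overall safety on everyone with an attempted procedure and has no rule for incomplete follow-up. Section 11.4: "Missing data will not be imputed unless otherwise specified".

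**The concern.** In a trial with continuing treatment, a withdrawal clause of this kind mainly stops exposure. Here, once the procedure is done, its main effect on the data is to stop observation. Several components of the primary safety endpoint take time to show. A hospital stay becomes prolonged, a sequela is judged permanent, or a patient dies, days or weeks after the event that started it.

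A subject who is doing poorly may miss visits, may be thought better off without them, or may be unable to continue. The grounds in Sections 8.7 and 8.8 can cover all three. Loss of follow-up may therefore be related to the outcome being measured. The people who decide know the assigned device, and one of them is the manufacturer of one of the two devices. At stake is the completeness of a primary endpoint in a study that Section 3.3 says will supply data for the initial CE Mark application.

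**Working it through.** The plan gives no figure to reproduce: Section 11.2 calls the sample size empirical and states no dropout rate. The check is mainly a reading of the follow-up path, with arithmetic for scale.

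**Step 1. Which withdrawals matter.** The intent-to-treat and safety sets (Sections 11.3.1 and 11.3.3) contain only subjects with an attempted procedure. A directed withdrawal before the procedure does not touch the safety analysis; one after it does.

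**Step 2. What is captured for a treated subject who is withdrawn.**

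| Period | Source of safety data | Captured? |
|---|---|---|
| Procedure to withdrawal | Assessments during and after the procedure, at discharge and at Day 7 (Sections 8.3 to 8.5); serious events reported within 5 working days of discovery (Section 10.5.1) | Yes, as far as the visits reached |
| Day of withdrawal | Day 30 assessments brought forward (Section 8.8) | Only if the subject agrees |
| Withdrawal to Day 30 | None required | Not assured |

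Section 10.5.1 covers all subjects at each contact, but after exit no contact is scheduled.

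**Step 3. What can be lost.** The endpoint is counted per subject. A subject who met one component before withdrawal is already counted, and later events do not change the arm's rate. The loss is confined to (a) a first qualifying complication after withdrawal and (b) an adverse event open at withdrawal that qualifies only later.

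**Step 4. Scale.** Inputs: 30 subjects per arm (Section 6.6), assumed all treated; k withdrawn with unknown outcome (k is an assumption); x events observed in the arm.

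- Shift from one missed event: 1/30 = 3.3 percentage points.
- Bounds on the arm's rate if the k unknown outcomes are all non-events or all events: x/30 to (x + k)/30.
- x = 0 and k = 1, 2, 3: 0 to 3.3%, 0 to 6.7%, 0 to 10.0%.
- x = 1 and k = 1: 1/30 = 3.3% if the withdrawn subject is counted as event-free, 1/29 = 3.4% if left out of the denominator, and 2/30 = 6.7% if that subject had an event. The plan does not say which of the first two would be reported.

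**Step 5. Against sampling error.** The exact 95% upper limit for 0/30 is 1 − 0.025^(1/30) = 11.6%. For 1/30 the exact 95% interval is 0.1% to 17.2%. One missed event is smaller than this uncertainty, but the interval does not allow for outcome-related loss.

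**The case against.** The strongest reply is that little is lost. Many major complications will be known from the procedure, discharge or Day 7. A subject too ill to attend has often already met the endpoint. Serious events go to the sponsor within days of discovery, and data up to withdrawal are kept. This stands, and it is why the point is limited to first or evolving events after withdrawal. It does not cover the interval to Day 30.

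Second, the text does not forbid later follow-up. The sentence on unresolved events is worded as a general rule, refers to study end, and describes care. The stop on study-specific procedures is written for subjects who choose to leave. A reader might infer that follow-up after exit is ruled out; the documents do not say so. They only fail to require it.

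Third, the clause has legitimate uses. Subjects count as enrolled at consent (Section 7.5), so it can apply before the procedure, and later it can spare an ill subject a clinic visit and blood draw. A reader might infer that withdrawal after Day 0 serves no purpose; that goes too far.

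Fourth, the study is descriptive, treated subjects stay in the safety set, and Section 11.4 permits a separate missing category. This lowers the stakes. However, neither a missing category nor imputation recovers an event that nobody looked for.

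**Conclusion.** The gap is real and limited. For treated subjects withdrawn by the investigator or sponsor, or exiting under Section 8.7, nothing assures safety ascertainment between exit and Day 30, and the loss may depend on outcome. Each missed event moves an arm by 3.3 percentage points. This assumes 30 treated subjects per arm and a 30-day horizon taken from Section 6.7, because Section 6.4.2 states no window of its own.

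Two stronger conclusions are tempting and not supported:

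- **That the complication rate will be understated, or understated more in one arm.** Selective loss is possible but not shown, and no withdrawal rate is given.
- **That one missed event equals nearly the whole expected rate**, using the 3.6% in Section 3.2. That figure covers portal vein puncture-related complications with the Cook sets. It is not the rate of the composite, and such injuries arise on Day 0, so they are among the events least likely to be lost this way.

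The wording should be changed, because unrecorded events may not be recoverable afterwards.

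**What to change.** In Sections 8.7 and 8.8, separate the end of visits from the end of safety data collection. For treated subjects:

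- Withdrawal directed by the investigator or sponsor, or early exit, ends study visits and tests only.
- Adverse events (including the outcome of those still open), readmission and vital status continue to be collected by phone or from the medical record through Day 30, unless the subject withdraws consent for this.
- The case report form records who initiated the withdrawal, why and when, and these are tabulated by arm.

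The fix stops at Day 30. Following open events to site close-out would make observation time depend on enrolment date and would exceed the stated follow-up, so it is not part of this point.

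Cost: wording in two sections, matching consent text, and phone or chart follow-up of what should be a few subjects. The sample size and the subject's right to withdraw are unchanged.
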